#### **5.5.2.2. Mini-Hyper-CVD [Odd courses 1, 3, 5, 7]:**

- Cyclophosphamide (CTX) 150 mg/m^2 intravenously (IV) over 3 hrs ( $\pm 1$  hour) every 12 hrs x 6 doses on Days 1, 2, 3
- MESNA 300 mg/m^2/d IV continuous infusion daily for 24 hrs ( $\pm 4$  hours), starting approximately 1 hour prior to CTX and completing by approximately 12 hrs after the last dose of CTX.
- Vincristine 2 mg IV on Days 1 ( $\pm 3$  days) and 11 ( $\pm 3$  days). Vincristine is not myelosuppressive and may be given while subjects are receiving a filgrastim product (G-CSF); no known adverse effects have been observed with the 2 agents given together. Biosimilars may be used for filgrastim or peg-filgrastim.
- Dexamethasone 20 mg IV or orally daily on Days 1 - 4 ( $\pm 3$  days) and Days 11 - 14 ( $\pm 3$  days).

- Filgrastim (G-CSF) 10 mcg/kg (rounded) subcutaneously daily (or 5 mcg/kg twice daily) until post-nadir granulocytes  $> 1.0 \times 10^9/L$  and may be stopped earlier for bone pain or other related toxicity. Minimum time allowed between courses is 14 days. Peg-filgrastim may replace filgrastim (G-CSF) at a dose of 6 mg SQ on Day 5 ( $\pm 3$  days). Biosimilars may be used for filgrastim or peg-filgrastim.
- For subjects with CD20 expression ( $\geq 20\%$  by flow cytometry) Rituximab 375 mg/m^2 may be added on Days 1 ( $\pm 3$  days) and 11 ( $\pm 3$  days) of Cycles 1 and 3. For subjects receiving rituximab all therapy can be moved back 1 day if needed (i.e. Day 1 starts Day 2, Day 2 starts Day 3, etc.).
- CNS prophylaxis: Methotrexate 12 mg intrathecally (6 mg via Ommaya reservoir) on Day 2 ( $\pm 3$  days) of Cycles 1 and 3. Cytarabine 100 mg intrathecally on Day 7 ( $\pm 3$  days) of Cycle 1 and 3 for a total of 8 intrathecal (IT) doses. These are generally given on Cycles 1 - 4 but if one or more IT treatments is missed it can be made up on a later cycle. Administer in 3 to 5 cc of preservative-free normal saline.

#### 5.5.2.3. **Methotrexate and Cytarabine [Even courses 2, 4, 6, and 8]:**

- Methotrexate (MTX) 50 mg/m^2 IV over 2 hrs ( $\pm 1$  hour) followed by 200 mg/m^2 over 22 hrs on Day 1. Total duration of administration is 24 hours (2 plus 22 hours) ( $\pm 3$  hours).
- Cytarabine 0.5 g/m^2 IV over 3 hrs ( $\pm 1$  hour) every 12 hrs for 4 doses on Days 2 and 3.
- Leucovorin rescue 50 mg IV or oral followed by 15 mg IV or oral every 6 hours for 8 doses (or until MTX level is less than 0.1  $\mu$ M) beginning 12 hrs ( $\pm 3$  hrs) post MTX completion (i.e. approximately 36 hours from start of MTX).
- Check MTX levels around time 0h, 24h and 48h post completion of MTX unless methotrexate cleared:
  - if  $> 20 \mu$ M at Time 0, hold cytarabine and repeat level; if continues to be  $> 20 \mu$ M reduce cytarabine to 0.25 g/m^2 IV over 2 hours every 12 hours for 4 doses on Days 2 and 3. Begin leucovorin rescue as described above.
  - if  $> 1 \mu$ M at 24hrs or  $> 0.1 \mu$ M at 48 hours, increase leucovorin rescue to 50 mg IV or oral every 6 hrs until serum methotrexate level is  $< 0.1 \mu$ M. Clearance to levels 0.15  $\mu$ M or less is acceptable in subjects with normal renal function.
  - Leucovorin rescue may be increased further for elevated methotrexate levels or delayed clearance
- Filgrastim (G-CSF) 10 mcg/kg (rounded) subcutaneously daily (or 5 mcg/kg twice daily) until post-nadir granulocytes  $\geq 1.0 \times 10^9/L$  and may be stopped earlier for bone pain or other related toxicity. Minimum time allowed between courses is 14 days (e.g., Day 14). Peg-filgrastim may replace filgrastim (G-CSF) at 6 mg SQ on Day 4 ( $\pm 3$  days). Biosimilars may be used for filgrastim or peg-filgrastim.

- For subjects with CD20 expression ( $\geq 20\%$  by flow cytometry) Rituximab 375 mg/m^2 may be added on Days 1 ( $\pm 3$  days) and 8 ( $\pm 3$  days) of Cycles 2 and 4. For subjects receiving rituximab all therapy can be moved back 1 day if needed (i.e. Day 1 starts Day 2, Day 2 starts Day 3, etc.).
- CNS prophylaxis: cytarabine 100 mg day 5 + 3 days and methotrexate 12 mg intrathecal (IT) (6 mg via Ommaya reservoir) Day 8 + 3 days of Cycle 2 and 4 for a total of 8 IT doses. These are generally given on Cycles 1- 4 but if one or more IT treatments is missed it can be made up on a later cycle. Administer in 3 to 5 mL of preservative-free normal saline

#### **5.5.3. Intrathecal Treatments**

If the subject has been previously treated, and has had prior intrathecal therapy, or prior CNS disease, discuss management of CNS with the Principal Investigator.

If active CNS disease: Consider methotrexate alternating with cytarabine twice weekly until cerebrospinal fluid (CSF) clear; then once weekly for 4 weeks, then every other week for 4 weeks, then monthly for 4 months. Alternative methods of treating CNS disease are allowed if appropriate for the subject (e.g., intrathecal liposomal cytarabine, or others).

Concomitant intrathecal chemotherapy should be avoided, if possible, on the days of administration of intravenous methotrexate and cytarabine (even courses).

#### **5.5.4. Suggested Standard Dose Reductions/Modifications/Discontinuations:**

- Vincristine 1 mg IV Days 1 and 11 (50% reduction) if:
  - Bilirubin  $> 2$  mg/dl and  $\leq 3$  mg/dl
  - Clinically significant grade 2 peripheral neuropathy persisting greater than 2 weeks.
  - Eliminate vincristine for Grade 3-4 peripheral neuropathy, including Grade 3-4 ileus suspected to be related to vincristine, or bilirubin  $> 3$  mg/dL.
- Methotrexate:
  - Consider reduction by 25% to 50% for Grade 3 or worse mucositis with previous methotrexate course.
  - Reduce by 50% for calculated creatinine clearance 10-50 mL/min, if  $< 10$  mL/min, hold methotrexate.
  - Reduce by 25% to 75% for delayed excretion and/or nephrotoxicity with previous methotrexate course.
  - Reduce by 50% for pleural effusion or ascites (drain effusion if possible).
- **Non-hematological toxicity**

- If Grade 3 or 4 non-hematologic toxicity is at least possibly attributable to DS-1594b, dose interruption of DS-1594b is required. Subjects who experience drug-related Grade 3 non-hematological toxicity may be given a subsequent course one dose level below the previous course, but the subject must have recovered to Grade  $\leq 1$  before start of the next course. If a subject has drug-related Grade 4 non-hematological toxicity, he/she may receive a subsequent courses at one reduced dose level after resolution of toxicity to Grade  $\leq 1$ , only if approved by the PI based on the clinical significance of the toxicity and only if subject has had derived a benefit from the therapy. The dose of DS-1594b can be decreased during a cycle, at the discretion of treating physician and PI, for chronic Grade 2 non-hematological toxicity. Other dose modifications may be considered as clinically indicated with documentation and approval of the PI.

- **Hematologic toxicity**

- Dose interruptions or modifications will be made for Grade 4 hematological toxicities, only if considered at least possibly related to DS-1594b and not related to underlying disease or the use of chemotherapy, as determined by the treating physician and the study PI. Subjects with baseline neutropenia or those who have significant bone marrow involvement may be particularly at high risk.
- If a subject achieves CRi or has a morphologically leukemia free bone marrow after completion of a cycle, DS-1594b may be interrupted from Day 21 for up to 14 days or until recovery of  $ANC \geq 0.5 \times 10^9/L$ . The next cycle administration will also be delayed until  $ANC \geq 0.5 \times 10^9/L$ . If DS-1594b is interrupted then the next cycle administration of chemotherapy will also be delayed. The next cycle with both DS-1594b and chemotherapy will resume on the same day after the interruption.
- If a subject presents with new onset Grade 4 neutropenia for more than 1 week during subsequent cycles, unless it is thought to be due to the underlying disease, DS-1594b dosing may be interrupted until ANC recovery to  $>0.5 \times 10^9/L$  in consultation with the study PI. DS-1594b may be re-initiated at a lower dose per discussion between the treating physician and the study PI.
- Other modifications of drug schedules may be implemented if judged to be in the best clinical interest of the subject after discussion with PI or at the discretion of the treating physician. This includes delays in chemotherapy cycles because of persistent myelosuppression, other side effects, subject request, or other reasons. Missed doses of DS-1594b do not need to be made up.
- Dose reductions exceeding those above or in other agents, e.g., leucovorin, antibiotics, antiemetics, etc., are allowed after discussion with the Principal Investigator.

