### 3.2.2. Dose-Limiting Toxicity Definition

Dose-Limiting Toxicity (DLT) is defined in this study as a non-hematologic adverse event or abnormal laboratory value assessed as unrelated to disease progression, intercurrent illness, or concomitant medications and occurring during the first 28 days on study that meets any of the following criteria, using the Common Terminology Criteria for Adverse Events (CTCAE) grading system, version 5.0:

- Hematologic DLT is defined as CTCAE Grade 4 neutropenia (absolute neutrophil count  $<0.5 \times 10^9 /L$ ) or thrombocytopenia (platelet count  $<25.0 \times 10^9 /L$ ) lasting for 42 days or more from Cycle 1 Day 1 in the absence of residual leukemia (i.e., with less than 5% blasts by morphology or residual leukemia by flow-cytometry).
  - Anemia will not be considered for the definition of DLT.
- CTCAE Grade 3 AST (SGOT) or ALT (SGPT) increased for at least 7 days or Grade 3 hyperbilirubinemia for at least 7 days.
- CTCAE Grade 3 AST (SGOT) or ALT (SGPT) increased accompanied by Grade 2 bilirubin increase
- CTCAE Grade 4 AST (SGOT) or ALT (SGPT) increased of any duration
- Any other non-hematological adverse events that are CTCAE Grade 3 or 4. However, the following adverse events are NOT considered DLTs:
  - Grade 3 nausea, vomiting and diarrhea will be considered DLT only if not controlled to Grade 2 or lower with optimal therapy within 72 hours (not including tube feeding, total parenteral nutrition, and/or hospitalization). Any Grade 3 gastrointestinal toxicity requiring tube feeding, total parenteral nutrition, and/or hospitalization and any Grade 4 gastrointestinal toxicity will be considered DLT.
  - Grade 3 or 4 biochemical abnormalities (e.g., lipase or amylase increased) will only be considered DLT if accompanied by clinical consequences.
  - Grade 3 or 4 isolated electrolyte abnormalities must be without clinical consequence and resolve, with or without intervention, to less than Grade 2 levels within 72 hours.
  - Grade 3 infusion reaction if successfully managed and which resolves within 72 hours
  - Grade 3 or 4 Tumor Lysis Syndrome if it is successfully managed clinically and resolves within 7 days without end-organ damage

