  - Grade 3 or 4 Differentiation Syndrome which improves to  $\leq$  Grade 1 within 7 days of the start date of  $\geq$  Grade 3 Differentiation Syndrome and which is not associated with end-organ damage. Note: Grade 1 is mild, Grade 2 is moderate, Grade 3 is serious, and Grade 4 is life-threatening.

- CTCAE Grade 3 QTcF prolongation (based on the average of 3 triplicate 12-lead readings or Holter monitor reading)
- Results in dose-reduction or discontinuation of therapy
- Any treatment-related death;
- Subjects not considered evaluable due to insufficient dosing (at least 75% of doses of study drugs) and who do not develop a toxicity that is considered a DLT will be replaced. These subjects may continue therapy on trial after discussion with the Principal Investigator if they are having clinical benefit and the reasons for continuation and potential benefit/risk profile for the subject must be clearly documented in the medical records.
- **Phase 2 only:** For subjects in venetoclax- or Mini-HCVD-containing regimens (cohorts C and D) who do not receive venetoclax or Mini-HCVD on Day 1 due to logistical and/or financial reasons, the DLT period will be extended to 28 days from the first dose of venetoclax or Mini-HCVD. For evaluation of hematologic-related DLT, the DLT evaluation period will be 42 days from the first dose of venetoclax or Mini-HCVD.
- Subjects must receive at least 75% of the doses of DS-1594b, azacitidine (Phase 2 only), venetoclax (Phase 2 only), or miniHCVD (Phase 2) during the first 28 days on trial (i.e. during Cycle 1) to be considered evaluable during the DLT evaluation period. Subjects who receive less than these planned number of doses of each drug during the first 28 days on trial will not be considered evaluable during the DLT evaluation period. However, if such subjects develop a toxicity that would normally be considered a DLT this will still be captured as a DLT. Any toxicity that meets the criteria for DLT during the first 28 days of trial in a subject who has received at least one dose of trial medication will constitute a DLT.
- For subjects who discontinue therapy, the reason for treatment discontinuation will be documented.
- Dose modifications other than the ones mentioned above can be considered after discussion with the PI and proper documentation of the rationale.

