## 3.3. Phase 2 Design

Enrollment in Phase 2 will start once the RP2D has been determined in Phase 1. This Phase 2 study will have four cohorts:

- Cohort A: DS-1594b monotherapy for R/R AML with MLL-r,
- Cohort B: DS-1594b monotherapy for R/R AML with NPM1m,
- Cohort C: DS-1594b in combination with azacitidine and venetoclax for R/R AML with NPM1m or MLLr
- Cohort D: DS-1594b in combination of mini-HCVD for R/R ALL with MLLr

Subjects enrolled in Cohorts A and B will receive the RP2D dose of DS-1594b determined in Phase 1. Cohorts C and D will enroll an initial 6 subjects in a safety run-in at one dose level below the RP2D (Dose level 0) with DS-1594b dose titration as specified below.

Cohorts A and B (single agent cohorts) will enroll a maximum of 26 subjects, and Cohorts C and D (combination cohorts) will enroll a maximum of 32 subjects, to allow reasonable determination of CRc within 3 months of therapy initiation.

For the combination cohorts (C & D) there will be a safety-run in evaluation with pre-defined toxicity stopping rules to be implemented for early DLT evaluation as per following plan:

- Safety run-in evaluation by the Safety Review Committee of the first 6 subjects in cohorts C and D will occur after 6 subjects have completed at least one cycle of treatment (or at least 28 days from the first day of treatment).
- Enrollment will be paused while the first 6 subjects are evaluated for safety. Each combination cohort will be evaluated independently.
  - If  $\leq 1$  of the 6 subjects experiences DLT in the first cycle of treatment, the treatment combination will be considered as safe and the DS-1594b dose can be escalated to the RP2D (Dose level 1) for the treatment of the next 6 patients (repeat the safety run-in evaluation). If the RP2D (Dose level 1) is considered safe, continue enrollment of an additional 20 subjects at the RP2D (i.e. total subjects treated at the RP2D will be 26 subjects; total cohort size will be 32 subjects). If  $\geq 2$  of 6 subjects at the RP2D experiences DLT in the first cycle of treatment, de-escalate and continue enrollment of an additional 20 subjects at Dose Level 0.

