  - If  $\geq 2$  of 6 subjects have DLTs in the first cycle of treatment at Dose Level 0, then an additional 6 subjects will enroll at a next lower dose level to be determined by the Principal Investigator and Safety Review Committee after reviewing the safety, efficacy, and PD data from the first 6 subjects enrolled ([Table 6](#)[Table 6](#), [Table 7](#)[Table 7](#)). If  $\leq 1$  of the additional 6 subjects treated at the lower dose level experience DLTs, this treatment combination will be considered as safe and continue to enroll to a total of 26 subjects (i.e. an additional 20 subjects at the lower dose level; total cohort enrollment of 32 subjects). If  $\geq 2$  of these 6 additional subjects experienced DLTs, then enrollment at the current dose level will be closed.
- Subjects must receive at least 75% of the doses of DS-1594b, azacitidine (Phase 2 only), venetoclax (Phase 2 only), or miniHCVD (Phase 2) during the first 28 days on trial (i.e. during Cycle 1) to be considered evaluable during the DLT evaluation period. Any subjects who are not evaluable for DLT in either cohort during the safety-run in period will be replaced for the assessment of DLT rate. This will allow for early identification of significant toxicities and early stoppage in the combination cohorts.
- The Safety Review Committee (SRC) will meet when there are enough DLT-evaluable subjects to review in each cohort who have completed the DLT evaluation period. The SRC will review the DLT data, other AE data, and available PK/PD, ECG, and laboratory data before proceeding to expansion of each of the cohorts to enroll the additional 20 subjects.

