#### **Azacitidine:**

Azacitidine (75 mg/m^2/day) will be administered subcutaneously (SQ) or intravenously (IV) for the first 7 days of every cycle. Azacitidine may be given in a 5on - 2off - 2on or 4on - 2off - 3 on or other similar modified schedule if the subject is not able to get weekend infusions. Azacitidine is administered in the clinic or chemotherapy administration area. Both SQ and IV forms of administration are FDA approved and are allowed and considered interchangeable. Subjects may start receiving azacitidine by one route and change to the other, and administration schedules from one schedule and change to the other at any time as needed based on subject and/or physician preference.

- In Cycle 1, subjects should undergo a bone marrow aspiration and biopsy on Day 21 (+/- 4 days). Subjects who achieve a confirmed marrow remission (i.e. bone marrow blasts  $< 5\%$  by morphology) or marrow aplasia/hypoplasia ( $\leq 10\%$  cellularity or insufficient sample) may discontinue venetoclax for the remainder of the cycle and be monitored for count recovery.
  - If the Day 21 bone marrow shows  $< 5\%$  blasts, the venetoclax may be held, and consider delaying cycle 2 till ANC  $> 0.5 \times 10^9/L$  and platelets are  $> 30 \times 10^9/L$  without platelet transfusion support for  $> 5$  days.
  - If the Day 21 bone marrow shows aplasia/hypoplasia ( $\leq 10\%$  cellularity or insufficient sample), the venetoclax may be held on Day 21 to avoid venetoclax related myelosuppression or further marrow hypo/aplasia, and a repeat bone marrow should be performed on Day 28 (+/- 4 days) to confirm response and MRD assessment. If the Day 28 bone marrow shows  $\geq 5\%$  blasts, proceed with Cycle 2 if this is in the best interest of the subject (those with C1D28 bone marrow  $\geq 5\%$  are allowed to receive 21 days of venetoclax in Cycle 2). If the Day 28 bone marrow shows  $< 5\%$  blasts, the venetoclax may be continued to be held, and consider delaying cycle 2 till ANC  $> 0.5 \times 10^9/L$  and platelets are  $> 30 \times 10^9/L$  without platelet transfusion support for  $> 5$  days. If the Day 28 bone marrow shows persistent aplasia/hypoplasia ( $\leq 10\%$  cellularity or insufficient sample) venetoclax may be held to avoid venetoclax related myelosuppression or further

marrow hypo/aplasia and consider repeating a bone marrow in approximately 10-14 days.

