### **5.5.2. Mini-Hyper-CVD Regimen**

#### **5.5.2.1. General Considerations**

- The Mini-hyper-CVD (odd cycles) will alternate with methotrexate and cytarabine (even courses) administered on Day 28 (if count recovery allows) or later day cycle (as count recovery allows).
- Anti-emetic therapy with each course of intensive chemotherapy as needed.

- Filgrastim (G-CSF) will be administered with each course after the completion of chemotherapy. Peg-filgrastim may replace filgrastim (G-CSF). Biosimilars may be used for filgrastim or peg-filgrastim.
- Next cycle may be started when granulocytes  $> 1.0 \times 10^9/L$  and platelets  $\geq 50 \times 10^9/L$ . Cycles may be started with dose reductions prior to full platelet recovery, if the treatment is delayed (e.g., greater than 28 days from last cycle).
- Prophylactic antibiotics may be given with each course until neutrophil recovery to  $0.5 \times 10^9/L$  or greater (or other antibiotics if being treated for active infection). Suggestions include: Levaquin 500 mg orally daily; trimethoprim-sulfamethoxazole double-strength one tablet orally twice daily; or other appropriate antibacterial agent. Caspofungin or another appropriate antifungal agent. Valacyclovir 500 mg orally daily; or acyclovir 200 mg orally twice daily; or another appropriate antiviral agent.
- Omit azoles on Day -1, same day, and day after vincristine.
- In general, 8 cycles of chemotherapy (4 Mini-hyper-CVAD, 4 methotrexate plus cytarabine) will be administered in approximately 28-day intervals (depending on the recovery of blood counts). Thereafter, maintenance therapy with DS-1594b in combination with, vincristine and corticosteroids may be continued for up to 2 years of maintenance. Modifications thought to be in the best interest of the subject are allowed after discussion with the Principal Investigator. Subjects will be followed indefinitely for relapse and survival.
- For subjects with CD20 expression ( $\geq 20\%$  by flow cytometry) Rituximab 375 mg/m^2 may be added on Days 1 ( $\pm 3$  days) and 11 ( $\pm 3$  days) of Cycles 1 and 3, and on Days 1 ( $\pm 3$  days) and 8 ( $\pm 3$  days) of Cycles 2 and 4. For subjects receiving rituximab all therapy can be moved back 1 day if needed (i.e. Day 1 starts Day 2, Day 2 starts Day 3, etc.).
- Methotrexate dose regimen will be adjusted as indicated below for pleural effusions.

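### In the Cohort C and D safety run-ins, the six-subject dose decision may be taken at 28 days, although the hematologic DLT cannot be met before Day 42

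*Combined protocol and SAP*

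**What the plan says.** **The DLT definition (Section 3.2.2).** The opening sentence confines DLTs to the first 28 days, and a later bullet again makes a qualifying toxicity in those 28 days a DLT. The hematologic criterion is ANC below 0.5 or platelets below 25 (x10^9/L) "lasting for 42 days or more from Cycle 1 Day 1 in the absence of residual leukemia". One further bullet covers Cohort C and D subjects who do not receive venetoclax or mini-HCVD on Day 1. For them the 28-day period runs from the first dose of that drug, and then: "For evaluation of hematologic-related DLT, the DLT evaluation period will be 42 days from the first dose of venetoclax or Mini-HCVD". There is no matching sentence for subjects who start on time.

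**The run-in (Section 3.3).** The review of the first six subjects "will occur after 6 subjects have completed at least one cycle of treatment (or at least 28 days from the first day of treatment"). If at most 1 "of the 6 subjects experiences DLT in the first cycle of treatment, the treatment combination will be considered as safe", and DS-1594b may go up to the RP2D for the next 6. With 2 or more DLTs the dose goes down. The same section says the Safety Review Committee meets when there are enough evaluable subjects "who have completed the DLT evaluation period", and that it also reviews laboratory data.

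**Starting Cycle 2.** In Cohort D with CRi or leukemia-free marrow, Section 5.5.4 says "The next cycle administration will also be delayed until" ANC is at least 0.5, with no platelet figure. Section 5.5.2.1 asks for granulocytes above 1.0 and platelets of at least 50, and adds: "Cycles may be started with dose reductions prior to full platelet recovery, if the treatment is delayed". Section 6.2.1 allows courses in the first three cycles whatever the counts. In Cohort C the azacitidine text of Section 5.4.1 names both lineages after a Day 21 marrow remission: "the venetoclax may be held, and consider delaying cycle 2 till ANC" is above 0.5 and platelets are above 30.

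**The concern.** A criterion that needs 42 days of cytopenia cannot be met inside a 28-day count. If the committee decides when the sixth subject reaches Day 28, that subject cannot yet have a hematologic DLT, and neither can any other subject short of Day 42. Cycle 2 chemotherapy may also have begun by Day 42, and no text says whether the reading then still stands.

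These are the first combinations of DS-1594b with other agents, and both backbones are myelosuppressive. The 2-of-6 rule sets the dose for the next 6 subjects and then for 20 more. The later Bayesian toxicity monitoring (Section 9.3) leaves out the first six run-in subjects of Cohorts C and D, so a late DLT among those six has no stated later rule that picks it up.

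**Working it through.** **1. The plan's own figures.** The run-in rule has no stated operating characteristics. The nearest figures are those for the Section 9.3 toxicity monitoring. With a beta(0.5, 0.5) prior and the cutoff Pr(P_T > 0.2) > 0.85, the stopping boundaries come out at 4/10, 5/15, 6/20 and 8/26, as in Table 22. An exact binomial recursion over the looks at 10, 15 and 20 gives early-stop probabilities of 0.0235, 0.2509, 0.6360, 0.8954 and 0.9834 at DLT rates 0.1 to 0.5, as in Table 24. Those tables are correct as calculations and are not at issue.

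**2. Day arithmetic.** From the earliest review to the earliest hematologic DLT: 42 - 28 = 14 days. In Cohort D, Cycle 2 may start on Day 28 if counts allow. A DS-1594b hold from Day 21 of up to 14 days ends at Day 35, and 42 - 35 = 7 days. The decision and Cycle 2 can therefore both precede Day 42.

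**3. Subjects unread at the review.** Spacing is an assumption, because the documents give no accrual rate. When the sixth subject reaches Day 28, days on study for the six are:
- 14-day spacing: 28, 42, 56, 70, 84, 98, so 1 is short of Day 42.
- 7-day spacing: 28, 35, 42, 49, 56, 63, so 2 are short of Day 42.

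**4. Chance that the decision changes.** Let t be the total DLT rate, h the part that is hematologic and readable only at Day 42, and q = t - h. The values of t and h are assumptions. The quantity is the unconditional chance of at most 1 DLT counted at the review but at least 2 of 6 once all are read.

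One unread: h x 5t(1-t)^4, that is, a late DLT in the unread subject and exactly one DLT among the other five.
- t = 0.30: 5 x 0.30 x 0.2401 = 0.360. Times 0.05 gives 0.018; times 0.10 gives 0.036.
- t = 0.20: 5 x 0.20 x 0.4096 = 0.410. Times 0.05 gives 0.020; times 0.10 gives 0.041.

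Two unread: 4t(1-t)^3 x [(1-q)^2 - (1-t)^2] + (1-t)^4 x [2qh + h^2].
- t = 0.30, h = 0.05: 0.4116 x 0.0725 + 0.2401 x 0.0275 = 0.036.
- t = 0.30, h = 0.10: 0.4116 x 0.15 + 0.2401 x 0.05 = 0.074.
- t = 0.20, h = 0.05: 0.4096 x 0.0825 + 0.4096 x 0.0175 = 0.041.
- t = 0.20, h = 0.10: 0.4096 x 0.17 + 0.4096 x 0.03 = 0.082.

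If late hematologic DLTs are rarer, at h = 0.02 with one unread: 0.02 x 0.360 = 0.007 and 0.02 x 0.410 = 0.008.

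**5. What the word lasting already settles.** A subject who meets Section 5.5.2.1 in full before Cycle 2 no longer has a Grade 4 cytopenia, so there is no DLT. ANC of at least 0.5 under Section 5.5.4 ends the neutrophil limb in the same way. Two situations stay open in Cohort D. Platelets may be below 25 when Cycle 2 starts, under the platelet waiver of Section 5.5.2.1 or under Section 5.5.4 taken alone. And if Section 6.2.1 applies to Cohort D, either lineage may still be low. Attribution in these subjects is not quantified, because later chemotherapy could bias it in either direction.

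**The case against.** The best defence is that Section 3.2.2 does contain a 42-day hematologic period, and Section 3.3 has the committee meet on subjects who have completed the evaluation period. Twenty-eight days is a minimum, laboratory data are reviewed, and an ongoing Grade 4 cytopenia would be visible. Passing Dose Level 0 leads to a second six-subject run-in at the RP2D, whose late DLTs can still count at the look at 10 subjects. Section 8.10.1 requires prolonged myelosuppression to be recorded.

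Much of this stands. The committee is free to wait, and the text conflicts rather than being silent. But the 42-day sentence belongs to the late-start bullet, and evaluability is tied elsewhere in Sections 3.2.2 and 3.3 to the first 28 days, so waiting is permitted and not clearly required.

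The objection on size also has force. Every figure in the working assumes the committee decides without the pending reading. A total DLT rate of 20% is the plan's own tolerated level, so a reversal there is not clearly a wrong decision corrected. The DLT also requires absence of residual leukemia. Against the 25-40% response rates in Section 9.3, h of 10 points would mean roughly 10/40 = 25% to 10/25 = 40% of responders. That ratio is only a loose guide, since CR and CRh exclude such counts in Cohort C, but no document supports a rate that high.

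A reader might infer that the Cohort D rules for Cycle 2 contradict each other at ANC 0.5-1.0. They need not: Section 5.5.4 sets a floor, Section 5.5.2.1 says when a cycle may start, and a subject can satisfy both.

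A reader might also want larger reversal chances. Enrollment 3 days apart leaves five unread and gives 9.4-19.8% under the same assumed rates. That needs six subjects in 15 days. Section 2.2 puts KMT2A rearrangement at about 5% of ALL, Section 8.10.2 is headed for a single-site protocol, and nothing in the documents supports such accrual.

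**Conclusion.** The point holds for both combination cohorts. The run-in trigger and the first-cycle count do not fit a DLT defined over 42 days, and the one sentence that would reconcile them is written for late starters only. Under the assumed rates (t of 20-30%, h of 5-10 points), a changed decision has a chance of about 2-4% with one subject unread and 4-8% with two, falling to about 0.7-0.8% at h of 2 points with one unread. Rates and spacing are assumptions.

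The literal text might be taken to mean that hematologic DLTs are excluded from the run-in for good. With t = 0.30 and h = 0.10 that would raise the chance of passing from 0.420 to 0.655. The documents do not support this as the intent: they define a hematologic DLT, give it a 42-day period in one bullet, and tell the committee to use completed evaluation periods.

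The rules for starting Cycle 2 in Cohort D need a clarification only. No effect on the response endpoints or on Tables 22-26 is claimed.

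**What to change.** In Sections 3.2.2 and 3.3, state that for every run-in subject in Cohorts C and D the hematologic DLT window is 42 days from Cycle 1 Day 1 (from the first venetoclax or mini-HCVD dose for late starters, as now written). State that it is read at Day 42 whether or not Cycle 2 has started, and that it counts in the 2-of-6 rule.

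Add a hold. If at the review a run-in subject has unresolved ANC below 0.5 or platelets below 25 without residual leukemia, and 0 or 1 DLTs have been counted, the dose decision waits for that subject's Day 42 reading or earlier recovery. With 0 counted, one unresolved subject cannot bring the total to 2, so the hold is needed only if counted plus unresolved subjects reach 2. Chemotherapy is not delayed for the measurement, and no DLT is called before its definition is met.

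For Cohort D, say how Sections 5.5.2.1, 5.5.4 and 6.2.1 combine for starting Cycle 2. Cover whether a platelet condition applies in CRi or leukemia-free marrow, and whether Section 6.2.1 applies at all.

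The cost is wording, plus up to 14 more days of an enrollment pause that already exists, and only when the reading could change the decision. No tests are added: Section 8.3 already has blood counts twice weekly in Cycle 2.
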